#### Ancillary Outcomes:

**Histological Epithelial Coverage:** The presence/absence of a continuous epithelialized tissue will be determined from the Week 4 biopsy using routine histology and staining. The percent of subjects with complete epithelialized layer between the two groups will be compared using non-equivalence of the two proportion test. If the EVPOME and POM groups give a common proportion of about 75% epithelial coverage, then the standard error of the estimate of the difference between the EVPOME and POM groups is about 11% based on 30 subjects per group. This gives a margin of error of about 22% for a 95% confidence interval. The primary test will be based on a two-proportion test where a lower bound for the power can be determined by the power associated with binomial comparisons with  $n = 30$  in each group. If the true epithelial coverage of 75% is assumed at 4 weeks, and if we consider that a difference in epithelial coverage as large as 36.5% in favor of POM would still allow the EVPOME to be non-inferior, the proposed sample size of 30 per group would give 80% power to confirm non-inferiority and a one-sided confidence level of 97.5%.

**Vascular Ingrowth:** The degree of vascular in growth noted on the Week 4 biopsy specimen will be compared based on ordinal microvessel vascular in-growth from the IHC data. It is expected there will be utilization of the full range of the four point scale (labeled 1 through 4) and that a standard deviation of 1 unit might conservatively be expected. The margin of error for a 95% confidence interval will be 0.51 based on two sample sizes of 30 each. For the comparison between EVPOME and POM, the sample size will allow us to detect a difference as large as 0.72 units with 80% power using a 0.05 level test.

**Laser Doppler Flow (LDF):** LDF data will be compared based on gingival blood flow at Week 4 post-surgery at the graft site between the EVPOME and POM groups. One aspect of this study will be to examine and explore the usefulness of this measure. In particular, we will explore the use of control measures taken on normal tissue to help adjust for intra subject factors contributing to the variability. The primary investigation will compare gingival blood flow at the graft site at two weeks, four weeks, eight weeks, and 24 weeks post-surgery to the values in an analysis of covariance (ANCOVA) model. The corresponding differences at the control site will also be incorporated as a covariate to partially adjust for intra-individual variability. More detailed analyses will utilize ANCOVA methods for repeated measures. There is relatively little background data on the use of LDF to measure perfusion in the context being studied here though some preliminary data on measuring gingival blood flow can be found in Justus et al. where change in gingival blood flow from baseline to post surgery (over the period 7 to 24 .days) was found to have a mean of about -25 perfusion units (PU) with an SD of about 60 PU. The measurement is highly variable.

For repeatedly measured data such as pain and wound healing index, data will be

summarized by treatment groups at each follow-up time. In addition, linear mixed-effects models will be used to make the between group comparison while adjusting for potential within person correlation of the outcome variables. By using the modeling approach, it will be possible to incorporate all observations from both treatment groups and make between treatment group comparisons efficiently using a treatment dummy indicator. The model will allow us to not only compare the time-averaged means, but also allows us to explore the rate of decline between the EVPOME and POM groups such as the rate of decline in pain, using appropriate interactions terms. When appropriate, comparisons between treatments will be adjusted for surface area of the graft as well as measures of its geometry, and other variables including age, general health and alcohol use.

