## 9.5 Data Analyses

The main aim of the study is to determine by quantitative outcome measures that EVPOME will function as well as POM in terms of increased epithelialized tissue, decreased contracture, and increased microvessel infiltration. It is also expected that the EVPOME will have a closer adaptation in color rendition to the surrounding tissue. Our primary comparisons will be based on the observations at four weeks post-graft.

**AIM 1 - Keratinized Tissue:** Primary comparison will be based on week 4 assessment using an equivalence test of means. Background data on measurements of keratinized tissue for POM (standard of care) gave a mean measurement of 3.70 mm with an SD of 0.65 mm. The mean and SD were relatively constant over the follow up period from 3 to 12 months. If, in this study, both EVPOME and POM give comparable results, the distribution of the mean difference in keratinized tissue with 30 subjects in each arm will be approximately normal with a mean of 0 and standard error of 0.17, and a 95% confidence interval for the true mean difference between the two procedures will have a margin of error of about 0.33 mm. This confidence interval will exclude a value for the mean difference of 0.55mm or larger with probability at least 80%. Therefore sample size will be adequate to show near equivalence of the two treatments if the degree of keratinized tissue measurement of EVPOME is within  $\pm 0.55$ mm of POM. Statistical power will be even larger if non-inferiority of EVPOME to POM is desired, where true increase in keratinized zone in EVPOME group is no less than 0.55 mm compared with the increase of zone of keratinized tissue in POM.

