**AIM 2 - Shrinkage in Graft:** The percent shrinkage (contracture) in graft will be expressed as  $100*(1 - (\text{Area final}/\text{Area Day0}))$ , and the comparison will be based on week 4 assessment using an equivalence test of means (with log transformation if the data are highly skewed upon visualization). Prior data for POM gave a mean shrinkage of 25% at 4 weeks post-op with a standard deviation (SD) of about 13%. If shrinkage is about the same for both EVPOME and POM, with a sample size of 30 subjects in each group, this translates into an estimate of the mean difference with standard error of about 3.4%. This gives a margin of error of 6.6% for a 95% confidence interval, and the 95% confidence interval excluding a value for the mean difference in shrinkage as large as 11% with probability of 80%.

**Wound Healing Index (WHI):** WHI will be analyzed via the following chart, and the index will be tabulated by treatment group at follow-up visits 5, 6, 7, and 8. Depending on the observed distribution of the index, the data will either be dichotomized or considered as an ordinal data.

Scores	Criteria
1	Uneventful healing with no gingival edema, erythema, suppuration, patient discomfort, or flap dehiscence
2	Uneventful healing with slight gingival edema, erythema, patient discomfort, or flap dehiscence but no suppuration

3	Poor wound healing with significant gingival edema, erythema, patient discomfort, flap dehiscence, or any suppuration
---	---

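### Stated 80% non-inferiority power for histological epithelial coverage does not follow from its own inputs, which give about 90%

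*Combined protocol and SAP*

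**What the plan says.** The paragraph on histological epithelial coverage in Section 9.5 concerns the proportion of subjects whose week 4 biopsy shows a complete epithelial layer. It first takes a common proportion of 75% and reports that "the standard error of the estimate of the difference between the EVPOME and POM groups is about 11% based on 30 subjects per group". It continues: "This gives a margin of error of about 22% for a 95% confidence interval". It then sets the margin by saying that "a difference in epithelial coverage as large as 36.5% in favor of POM would still allow the EVPOME to be non-inferior", and concludes that "the proposed sample size of 30 per group would give 80% power to confirm non-inferiority and a one-sided confidence level of 97.5" percent. Earlier in the paragraph the groups are to be "compared using non-equivalence of the two proportion test".

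Two other calculations in Section 9.5 are useful for comparison. For keratinized tissue (Aim 1), planned as an equivalence test, the plan says: "This confidence interval will exclude a value for the mean difference of 0.55mm or larger with probability at least 80" percent. It adds: "Statistical power will be even larger if non-inferiority of EVPOME to POM is desired". For shrinkage (Aim 2), also an equivalence test, it refers to "the 95% confidence interval excluding a value for the mean difference in shrinkage as large as 11% with probability of 80" percent.

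**The concern.** Every input to the epithelial coverage power is printed in the paragraph, so the figure should be reproducible, and it is not. It also sits oddly beside Aim 1. There, a limit of almost the same size in standard errors is credited with at least 80% power for equivalence, and the plan notes correctly that non-inferiority would have more. In the coverage paragraph 80% is credited to non-inferiority itself.

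At stake is whether the planned conclusion for this outcome is clear. The margin and confidence level describe a one-sided non-inferiority claim, the power fits a two-sided equivalence claim, and the test name matches neither. That should be settled before the biopsy data are analysed.

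**Working it through.** **Inputs**, all from the coverage paragraph: proportion 0.75 in both groups (true difference 0), n = 30 per group, margin 0.365, one-sided level 0.025 (z = 1.960). Section 9.3 enrolls 66 to allow for up to 6 losses before week 4, so 30 per group needs no further deduction.

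**Step 1: reproduce the plan's precision figures.**

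- SE = √(2 × 0.75 × 0.25 / 30) = 0.1118, or 11.2 points (plan: about 11%).
- Margin of error = 1.96 × 0.1118 = 0.219, or 21.9 points (plan: about 22%).

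Both agree, so the variance model behind the paragraph is known.

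**Step 2: non-inferiority power with that SE.**

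- Power = Φ(0.365 / 0.1118 − 1.960) = Φ(3.265 − 1.960) = Φ(1.305) = 0.904. The plan states 0.80.

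**Step 3: other non-inferiority methods at the same inputs.**

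| Method | Power |
|---|---|
| Wald, enumerated | 91.0% |
| Farrington-Manning, enumerated | 91.6% |
| Newcombe interval, enumerated | 92.5% |
| Exact unconditional | 91.0% |
| Hauck-Anderson, enumerated | 88.2% |
| Wald with continuity correction, enumerated | 84.4% |

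None reaches 80%. With 27 per group (6 losses out of 60) the normal approximation still gives 87.2%.

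**Step 4: what 80% would require.**

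- Non-inferiority at 80% power needs a margin of 1.960 + 0.842 = 2.802 SEs. At 11.18 points per SE that is 31.3 points, not 36.5.
- With the margin kept at 36.5 points, n per group = 2 × 0.75 × 0.25 × 2.802² / 0.365² = 22.1, so 23. For 90% power it is 29.6, so 30, which is the planned number.

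**Step 5: compare with the equivalence calculations.** Equivalence power at a true difference of 0 is 2Φ(limit/SE − 1.960) − 1. For 80% the limit must be 1.960 + 1.282 = 3.242 SEs.

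| Outcome | SE | Limit | Limit/SE | Equivalence power | Non-inferiority power |
|---|---|---|---|---|---|
| Keratinized tissue | 0.65 × √(2/30) = 0.168 mm | 0.55 mm | 3.28 | 81.2% | 90.6% |
| Shrinkage | 13 × √(2/30) = 3.36 points | 11 points | 3.28 | 81.2% | 90.6% |
| Epithelial coverage | 11.18 points | 36.5 points | 3.26 | 80.8% | 90.4% |

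All three limits lie just above the 3.242 SEs needed for 80% equivalence power. For the first two outcomes the plan says 80% for an equivalence criterion, which is right. For the third it says 80% for non-inferiority.

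**The case against.** The strongest defence is that 80% was meant as a floor. Just before the power claim, the paragraph says that a lower bound on power can be found from a binomial comparison with 30 per group. The variance is largest at a common proportion of 50%, where power is Φ(0.365/0.1291 − 1.960) = 80.7%. A worst-case reading would therefore fit. It does not fit the text, which conditions the statement on 75% coverage and says the design would give 80%, not at least 80%. At 75% the binomial calculations give 84% to 92%.

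Other routes to about 80% exist, but they depart from what is printed. A variance pooled over 75% and 38.5% gives 81.4% (SE 12.8 points, margin of error 25.1). An unpooled variance at those proportions with a continuity correction gives 79.6% (SE 11.9, margin of error 23.3). The 50% case above has SE 12.9 and margin of error 25.3. None matches the stated 11% and 22%. A true EVPOME rate of 70% would give 78.1%, but the paragraph assumes a common rate.

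Three points on the other side stand:

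- About 90% is the normal-approximation result. The plan names no method, so the understatement is roughly 4 to 12 points.
- The comparison with Aim 1 suggests where the 80% came from but does not prove it.
- The margin's direction, the word non-inferior and the one-sided level all point to one-sided non-inferiority, so the test name reads most naturally as a slip.

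**Conclusion.** The stated power is wrong for the stated test. With 75% coverage in both groups, 30 evaluable subjects per group, a 36.5-point margin and a one-sided 2.5% level, non-inferiority power is about 90% (84.4% to 92.5% across methods), not 80%. The figure of 80% is about right for two-sided equivalence within ±36.5 points. The arithmetic does not depend on that explanation.

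The importance is low. The error is conservative, the outcome is ancillary, and Section 9.3 sizes the trial on the primary and secondary outcomes. The equivalence calculations for Aims 1 and 2 are sound on this point.

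**What to change.** Reword the one paragraph in Section 9.5 and state which claim is intended:

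- **If non-inferiority:** keep the 36.5-point margin, restate the power as about 90%, name the method used (or give the value for the test that will actually be run), and call the analysis a non-inferiority test of two proportions.
- **If equivalence:** say that the limits are ±36.5 points, that the test is two-sided equivalence, and keep about 80%.

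If 80% was intended as a worst-case floor, the text should say so and give the proportion at which it is reached. The cost is a wording change only. The sample size, margin, primary and secondary hypotheses and data collection are unaffected.

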### 5.1.9 Postoperative pain

Pain following the grafting procedure will be evaluated using a visual analog scale (VAS) at the time of palatal biopsy for the EVPOME and at the time of harvesting and grafting of the POM grafts.

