Women of childbearing potential must agree to use a medically acceptable means of birth control and test negative on the Screening Visit urine pregnancy test. Intraoral photographs will also be taken.

Lastly, upper and lower jaw impressions will be taken for stent fabrication to protect the donor site and for use in LDF measurements

Subjects randomized to Group 1 (EVPOME), will be scheduled for Visit 2 to undergo a palatal punch biopsy/tissue harvesting which will be the source of autogenous cells used to make the cellular component of the EVPOME, within 14 days of determination. Subjects randomized to Group 2 (POM) will bypass Visit 2 and proceed to scheduling of harvesting of palatal donor tissue graft and intra-oral grafting at recipient site (Visit 3) upon completion of screening procedures.

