#### 6.2.2 **Visit 2: Harvest Biopsy (EVPOME group only)**

At this time, a 6 mm in diameter supra-periosteal circular biopsy will be harvested for fabrication of the EVPOME from Group 1 subjects. Co-Investigators will perform the biopsy procedure. This biopsy will be performed at the school of dentistry research clinic. Intraoral photographs will also be taken at this time. A stent will be placed at this time if needed.

*Biopsy procedures:* All subjects will be prepped and draped in a sterile fashion prior to intraoral biopsies. Anesthesia will be obtained by local infiltrations and/or blocks. Tissue will be harvested using a 6mm punch. If bleeding is not controlled under gauze tamponade, a hemostatic collagen sponge will be placed and a cyanoacrylic dressing will be topically applied over the wound. Subjects will be given routine post-operative instructions to include a prescription for analgesia.

*Specimen handling:* The 6 mm biopsy specimen will be placed in a specifically prepared transport medium, containing 500.0ml DPBS (Dulbecco's Phosphate Buffered Saline) w/o  $\text{Ca}^{2+}$  &  $\text{Mg}^{2+}$  containing 0.54 g D-Glucose, 62.5 mg Gentamicin and 500.0  $\mu\text{g}$  Fungizone. The biopsy is immediately delivered to the CTML for oral keratinocyte dispersion and culture. The specimen will be labeled with pre-printed labels from the CTML with protocol number and subject study number.

A visual analog scale of pain will be taken at this time for group I and subjects will also be questioned about any adverse events.

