### 6.3.5 Clinical Assessments

Clinical assessments include width of keratinized mucosa (KM) as determined by the distance between the crest of the edentulous ridge, the gingival margin of the tooth, or the implant mucosal margin and the mucogingival line to the nearest millimeter, graft contracture, graft color as determined by assessing tissue perfusion, postoperative pain, Wound Healing Index (WHI), color of graft tissue compared to surrounding

3/28/2017

non-grafted tissue, and oral care follow-up. These assessments will be performed at post-operative visits 5, 6, 7 and 8. Periodontal measures include Periodontal Pocket Depth (PPD – measured from gingival margin to base of periodontal pocket to nearest millimeter), gingival recession measured from cemento-enamel junction on tooth to gingival margin, Clinical Attachment Level (CAL- determined by subtracting the gingival recession from PPD), and bleeding on probing (BOP) determined as present (1) or absent (0),

Visual analog scale for pain will be assessed for groups, I (at time of harvest of biopsy and EVPOME placement) and group II at time of harvesting of palatal donor graft and grafting at recipient site.

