## 9. STATISTICAL CONSIDERATIONS

### 9.1 General Design Issues

This is a randomized, parallel-group (autogenous *ex vivo* produced oral mucosa equivalent (EVPOME) vs. palatal oral mucosa (POM)) safety and efficacy study in subjects requiring additional keratinized oral mucosa for dental rehabilitation. The primary hypothesis is that EVPOME is an equivalent intraoral grafting material when compared to POM in regards to keratinized tissue and graft contracture, but is superior to POM in regards to pain, color rendition, and microvessel infiltration.

The comparison will be done using primary efficacy measures of enhanced keratinization, and secondary measures of graft contracture and wound healing index, and ancillary measures of increased microvessel ingrowth. Clinical assessments will include postoperative pain. Intraoral photographs will be done at screening and at biopsy, 2, 4, 8, and 24 weeks after intra-oral grafting. Tissue biopsy will be conducted at week 4 and laser Doppler flowmetry at weeks 2, 4, 8, and 24. Primary assessment time will be at week 4, and final assessments for all subjects will be at week 24.

Subjects will be screened until we have the necessary 60 enrolled. It is likely there will be 4 screened subjects to 1 enrolled subject. All subjects will undergo informed consent prior to any screening procedures. It is expected that it will take 2.5 years to successfully enroll 60 patients. Subjects will be recruited through the Patient Admitting and Emergency Services (PAES) clinic in the U-M School of Dentistry in conjunction with MCOHR. All new patients are routed through PAES and assigned to specialty or

undergraduate clinics. Most patients do not return to the PAES clinic, so we are not likely to have redundancy. PAES had 13,100 visits in 2003. It is estimated that 40% of the western population is missing 1 or more teeth (50% to be restored with implants for our purposes). Approximately 1/3 of them are in need of soft tissue oral mucosa grafts which is a very common procedure. This will give us a population from which to draw approximately 865 new patients per year. Of this group we need to recruit 60 subjects over two years from a potential pool of 1,730 patients. With an estimated enrollment of 1 out of 4 screened patients, we should have a pool of over 400 patients per year from which to select 30 subjects. Subjects will be recruited by full-time faculty members in the Department of Periodontics at the U-M School of Dentistry.

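### Section 5.1.9 conflicts with 6.3.5, 6.2.3 and the schedule on when EVPOME pain is measured, and Section 9.5 leaves open which VAS records and what form of time enter the pain comparison

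*Combined protocol and SAP*

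**What the plan says.** **Hypothesis.** Section 9.1 places pain among the outcomes on which EVPOME is expected to be "superior to POM in regards to pain, color rendition, and microvessel infiltration". Section 9.2.3 lists overall postoperative pain by VAS as an ancillary outcome, with no visit list and no main time point.

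**Timing of the VAS.** Section 5.1.9 says that it concerns pain after the grafting procedure, then gives the times as "at the time of palatal biopsy for the EVPOME and at the time of harvesting and grafting of the POM grafts". Section 6.3.5 gives them for groups "I (at time of harvest of biopsy and EVPOME placement) and group II at time of harvesting of palatal donor graft", so it adds EVPOME placement. Section 6.2.3 takes a VAS at Visit 3 (grafting) in both groups, and Sections 6.2.4 to 6.2.8 repeat it at Visits 4 to 8. The schedule in 6.1 marks the VAS at all eight visits.

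**Visit 2.** Section 6.2.2 states "A visual analog scale of pain will be taken at this time for group I", and Section 6.2.1 states "Subjects randomized to Group 2 (POM) will bypass Visit 2". The schedule puts Visit 2 at 2 to 40 days before grafting.

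**Analysis.** For repeated data such as pain, Section 9.5 plans summaries by group at each follow-up time. It adds a linear mixed model with which "it will be possible to incorporate all observations from both treatment groups", using a treatment indicator to compare time-averaged means and interaction terms to explore the rate of decline.

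**The concern.** Two gaps meet here. Read alone, 5.1.9 sets pain from a 6 mm punch against pain from palatal harvest plus recipient-site surgery, and leaves out pain at EVPOME placement. That is not pain after grafting in the EVPOME arm, and it is not what the other sections collect.

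Section 9.5 then does not settle which records form the comparison. The arms have different sets of VAS records, and both have one taken before any treatment. A time average over unequal visit sets can differ between arms when pain at every shared visit is the same. Superiority on pain is a stated hypothesis, so choosing the visits after the data are seen could change a reported conclusion.

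**Working it through.** The documents give no mean, SD, effect size or power for pain, so there is no planned figure to reproduce. All VAS values below are assumed (0-100 scale) and serve only to show size and direction. Differences are EVPOME minus POM.

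**1. When the VAS is taken, by section**

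| Source | EVPOME | POM |
|---|---|---|
| 5.1.9 | biopsy | harvest and grafting |
| 6.3.5 | biopsy and EVPOME placement | harvest and grafting |
| 6.2.1 to 6.2.8 | Visits 1-8 | Visits 1 and 3-8 |
| Schedule 6.1 | Visits 1-8 | Visits 1 and 3-8 (no Visit 2) |

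Planned records are therefore 8 per EVPOME subject and 7 per POM subject. From the first procedure onward they are 7 and 6.

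**2. Simple time average, Visits 1 to 8**

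Assume VAS 5 at Visit 1 and 40, 25, 15, 15, 5, 2 at Visits 3-8 in both arms, so the true difference is 0.

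- POM: (5 + 40 + 25 + 15 + 15 + 5 + 2)/7 = 107/7 = 15.3.
- EVPOME with Visit 2 pain of 5: 112/8 = 14.0, a false difference of -1.3.
- EVPOME with Visit 2 pain of 40: 147/8 = 18.4, a false difference of +3.1.

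**3. Random-intercept model with a treatment indicator and no visit effect**

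Assume 40, 30, 20, 15, 5, 2 at Visits 3-8 in both arms, mean m = 112/6 = 18.67, 30 subjects per arm. Add a Visit 2 record with pain b for EVPOME only.

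False difference = (6m + b)/7 - m = (b - m)/7.

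| Visit 2 pain b | False difference |
|---|---|
| 0 | -2.7 |
| 10 | -1.2 |
| 20 | +0.2 |
| 40 | +3.0 |
| 60 | +5.9 |

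Closed-form generalised least squares gives the same values at within-subject correlations of 0, 0.3 and 0.6.

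**4. Linear time with a treatment-by-time term**

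Same profile, Visit 2 placed at week -4. The fitted POM slope is -1.25 points per week. The fitted EVPOME slope is -0.68 if b = 0 and -1.76 if b = 60. The false slope differences are +0.57 and -0.51 points per week. At b = 20, where the false difference in step 3 almost vanishes, the slope difference is still +0.21.

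**5. What removes the distortion**

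- Visit 2 excluded: false difference 0 in both the treatment-indicator and the linear-time model.
- Visit 2 kept, visit as a categorical main effect: false difference 0.
- Visit 2 kept, with arm-by-visit terms: POM has no Visit 2 cell, so an average over all visits cannot be estimated for POM.

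**6. Visit 1 as an outcome**

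Randomised arms are expected to be equal before treatment. If a true difference d holds at Visits 3-8 and Visit 1 is averaged in, the contrast becomes (0 + 6d)/7 = 0.86d. This dilutes a true effect; it does not create one.

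**The case against.** A reader might infer three stronger points, and the documents support none of them.

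- **That the planned model does pool Visit 2.** Section 9.5 says only what the model makes possible and never names Visit 2. The same paragraph speaks of follow-up times, the outcome is called postoperative pain, and the synopsis counts five post-operative visits, which are Visits 4 to 8. A post-graft reading is at least as natural. What stands is that no visit list is given. In the same section, the Wound Healing Index is tied to Visits 5 to 8 and laser Doppler flow to weeks 2, 4, 8 and 24.
- **That the comparison is built to favour EVPOME.** This needs 5.1.9 to be read alone. That section says when the VAS is taken and sets no contrast between arms, and like-for-like records at grafting are already scheduled. The model distortion can also go either way.
- **That the arms have different time origins.** The schedule counts time from grafting as Day 0 in both arms. Visit 2 simply lies at negative time.

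There is also a fair objection to dropping Visit 2 altogether. The POM score at Visit 3 includes donor harvest, while EVPOME donor-site pain falls at Visit 2. A contrast from Visit 3 onward therefore counts donor-site pain on the day of harvest in one arm only. Less donor-site morbidity is one of the advantages that Section 1.1 claims for the tissue-engineering approach, so total procedure burden is a legitimate target. This objection stands and shapes the fix.

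Finally, pain is ancillary and unpowered, and the rate of decline is exploratory. That limits the weight of the point, but the superiority hypothesis in 9.1 remains.

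**Conclusion.** The point holds as a conflict between sections and an under-specified analysis. Section 5.1.9 does not agree with its own stated aim or with 6.3.5, 6.2.3 and the schedule. Section 9.5 does not say which VAS records enter, how Visits 1 and 2 are treated, or how time is modelled.

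If Visit 2 entered without a visit effect, the false arm difference would be about -1.3 to +3.1 points under one assumed profile and -2.7 to +5.9 under the other. Biopsy pain below the average of the other visits would flatter EVPOME on the time average, and biopsy pain above it would do the reverse. These sizes rest wholly on assumed VAS values, on Visit 2 being included, and on the absence of a categorical visit effect. The documents settle none of the three. The primary comparison of keratinized tissue is not affected.

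**What to change.** 1. Correct 5.1.9 to include the VAS at EVPOME placement, so that it agrees with 6.3.5, 6.2.3 and the schedule.
2. In 9.5, define the pain comparison on the visits that both arms share from grafting onward (Visits 3 to 8). Count time from grafting, enter visit as a category with arm and arm-by-visit terms, and use the Visit 1 VAS as a baseline covariate, not as an outcome.
3. Report Visit 2 pain in the EVPOME arm beside the Visit 3 contrast, or pre-specify a comparison of total procedure burden as supportive, so that EVPOME donor-site pain is not lost.

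The cost is wording only. Every VAS record needed is already in the schedule. The changes should be in place before the data are analysed.
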